4 STUDY PLAN

4.1 Study Design

This is a randomized, double-blind, placebo-controlled, single-dose, parallel-group study to assess the efficacy, safety, and tolerability of a single-dose IA administration of UBX0101 in patients with moderate to severe painful knee OA. Approximately 180 patients will be randomized (1:1:1:1) to one of four treatment groups (approximately 45 patients per group), all administered by IA route at Week 0. The four treatment groups will be enrolled concurrently.

Group 1: Placebo

Group 2: UBX0101 0.5 mg

Group 3: UBX0101 2.0 mg

Group 4: UBX0101 4.0 mg

Approximately 40 patients per group are expected to complete the Week 12 visit, assuming a 10% dropout rate. Study Drug will be administered as a single 8 mL IA injection at Week 0, Day 1. The primary endpoint analysis will be the change from baseline to Week 12 of the WOMAC-A score in patients receiving a single 0.5, 2.0, or 4.0 mg dose of UBX0101 versus those receiving placebo.

4.2 Design Element Rationale

Data from the Phase 1 study of UBX0101 in OA (Study UBX0101-OAR-101) suggest that administration of a senolytic agent to patients with moderate to severe painful knee OA can produce clinically meaningful improvement in pain and physical function that is sustained for at least 12 weeks after a single dose IA injection of UBX0101. This Phase 2 protocol is designed to confirm in a larger sample size the significant and durable treatment effects observed in Phase 1 and to further explore the doses of UBX0101.

Randomized, Double-Blind, Single-Dose, Placebo-Controlled Parallel-Group Design

To minimize selection bias, the study population will be randomly distributed to four parallel treatment groups. The study population will be treated and followed in a double-blinded manner to ensure that neither the patients nor the Investigator and study team evaluating the patients are biased by knowledge of the treatment received. One measure of maintaining the blind is for all Study Drug injections to be prepared as 8 mL volume solutions so that the blinded administrator of the IA injection is administering Study Drug that is matched for volume and clear, colorless appearance. Another measure to maintain the blind and minimize patient and evaluator bias is to perform all assessments uniformly on all patients, e.g., blood draw for measuring plasma UBX0101 level in placebo and UBX0101-treated patients alike.

Placebo Control

Placebo IA added onto stable background oral medications is the comparator in the study, because there is no universally accepted active comparator treatment for the refractory OA population under study. It is essential to include a placebo comparator group in parallel in the study to accurately describe the treatment effect of UBX0101 adjusted for the amount of placebo response, which is well described in clinical studies of arthritis pain. Lastly, the placebo comparator is useful for evaluating the incidence of safety events in the active UBX0101 groups compared to the incidence of events in the placebo group.

UBX0101

Study Duration

The 24-week treatment and follow-up period allows for an assessment of the longer-term durability of the treatment effect of single doses of UBX0101. Results from the Phase 1 study suggested that single-dose administration of UBX0101 2.0 and 4.0 mg led to improvements in pain and function, which were sustained through the last study visit at Week 12.

WOMAC-A Score as the Primary Endpoint

WOMAC-A is a well-established, validated instrument for measuring pain in knee and hip OA that has been commonly used as a primary or major secondary outcome in many OA clinical studies. WOMAC-A has content validity because it is a composite of five questions about different situations when knee OA pain may manifest itself. Analysis of the change from baseline in WOMAC-A in the Phase 1 study suggested a dose response with increasing doses of UBX0101.

5 POPULATION

5.1 Recruitment

Approximately 180 patients are planned for randomization in this study, anticipating approximately 160 patients, representing 40 patients per treatment group, to complete the Week 12 assessments.

5.2 Definitions

Patients officially enter the Screening period after providing informed consent.

A screen failure is a consented patient who has been deemed ineligible on the basis of one or more eligibility criteria or who has withdrawn consent prior to treatment assignment. Patients will be permitted to re-screen on a case-by-case basis, in consultation with the Sponsor's medical monitor.

An enrolled patient is one who has been deemed eligible and has been randomized and treated to a treatment group.

5.3 Inclusion Criteria

To be included in this study, each individual must satisfy all of the following criteria:

- Patients who are ambulatory with a diagnosis of OA of the knee, as defined by the American College of Rheumatology (ACR) Criteria (based on clinical and radiologic ACR criteria for at least 6 months; see Appendix 1) and who have baseline pain with a mean of ≥ 4 and ≤ 9 on the 11-point (0–10) average daily pain NRS for at least five of seven days during the Screening period.
- 2. Patients with a KL grade of 1–4 based on central reading of a weight-bearing radiograph of target knee.
- Patients aged ≥ 40 and ≤ 85 years.
- 4. Patients are permitted but not required to use an oral NSAID, serotonin and norepinephrine reuptake inhibitors (SNRIs) such as Cymbalta® (duloxetine), tramadol, or acetaminophen, provided that they have been taking a stable dose and regimen of medication for at least 4 weeks prior to Screening.
- 5. Patients with type 2 diabetes mellitus can be included as long as they are under adequate control (screening hemoglobin A1c ≤ 8.0) and have no evidence or history of diabetic neuropathy.
- Patients who have the capacity to give informed consent and who are willing and able to comply with all study-related procedures and assessments. Patients who do not have the legal capacity or medical competency to give written informed consent are ineligible for this study; consent via legally authorized representative is not accepted.

5.4 Exclusion Criteria

An individual is ineligible for this study if he or she meets any of the following criteria:

Patients with any condition, including laboratory or imaging findings and findings in the
medical history or in the pre-study assessments, that in the opinion of the Investigator or
the Medical Monitor constitutes a risk or contraindication for participation in the study or
that could interfere with the study objectives, conduct, or evaluation or prevent the
patient from fully participating in all aspects of the study.

- Patients with a body mass index (BMI) ≥40 kg/m² or a body habitus that precludes the MRI
- Patients with clinically significant co-existing conditions of the cardiovascular, renal, gastrointestinal, respiratory, nervous (e.g., neuropathy), metabolic, hematologic, or immune system.
- Patients with fibromyalgia based on ACR criteria (Wolfe et al. 2010; Wolfe et al. 2011).
- 5. Patients with any active, known, or suspected systemic autoimmune disease with musculoskeletal involvement (except for vitiligo, residual autoimmune hypothyroidism requiring only hormone replacement, psoriasis not requiring systemic treatment for 2 years, or conditions not expected to recur in the absence of an external trigger) or any history of a systemic inflammatory arthritis, such as rheumatoid arthritis, psoriatic arthritis, ankylosing spondylitis or spondylitis, or reactive arthritis.
- 6. Patients who have received IA treatment in the target knee with steroids or hyaluronic acid derivatives within the last 16 weeks prior to Screening, or with extended-release corticosteroid (e.g., Zilretta®) within the last 20 weeks prior to Screening.
- 7. Patients who are using a topical NSAID or topical analgesics on the target knee.
- Patients who are receiving anticoagulants (e.g., low molecular weight heparin or warfarin), factor Xa inhibitors (e.g., Eliquis[®]/apixaban), or P2Y12 inhibitors (e.g., Plavix[®]/clopidogrel or ticagrelor).
- 9. Patients who are receiving chronic oral corticosteroids.
- 10. Patients who have used opioid analgesics, marijuana or marijuana-derived products (e.g., cannabidiol), and topical capsaicin on the target knee within 8 weeks prior to Screening and at all times during the study.
- 11. Patients with a history of traumatic knee injury to the target knee, including, but not limited to, patients with meniscal root tear, within 2 years of study entry.
- 12. Patients who have undergone diagnostic arthroscopy to the target knee in the previous 6 months.
- 13. Patients who have undergone arthroscopic surgery (including microfracture and meniscectomy) on the target knee in the last 2 years prior to the Screening visit or are anticipated to have arthroscopic surgery on either knee at any time during the study period.
- 14. Patients with a history of previous total or partial knee arthroplasty.
- 15. Patients with an effusion at the Screening visit, which, in the opinion of the Investigator following examination and discussions with the patient, requires drainage for symptom relief.
- 16. Patients who have had regenerative joint procedures on any joint, including, but not limited to, platelet-rich plasma injections, stem cell transplantation, autologous chondrocyte transplantation, or mosaicplasty.
- 17. Patients with abnormal alanine aminotransferase or aspartate aminotransferase > 2 × upper limit of normal (ULN) at Screening.
- 18. Patients with bilirubin ≥ 2 × ULN at Screening.
- 19. Patients with renal dysfunction as defined by a glomerular filtration rate ≤30 mL/min/1.73 m² by laboratory testing (Chronic Kidney Disease Epidemiology Collaboration method) (Levey et al. 2009).
- 20. Patients with active or untreated hepatitis B or C or any history of human immunodeficiency virus infection at Screening.
- 21. Patients with any known active infections, including suspicion of IA infection and/or predisposition to infections due to immune system compromise.

- 22. Patients with a history of malignancy within 5 years and/or current evidence of active malignancy, except basal cell carcinoma, squamous cell carcinoma of the skin, and completely excised cervical intraepithelial neoplasia.
- 23. Patients with a history of drug or alcohol dependence within the last 3 years.
- 24. Patients with secondary arthritis that involves the target knee or would confound assessments of knee OA, e.g., joint dysplasia, chronic or recurrent crystal-induced arthritis (gout, calcium pyrophosphate deposition disease, podagra, etc.), aseptic osteonecrosis, acromegaly, Paget's disease, Ehlers-Danlos syndrome, Gaucher's disease, Stickler's syndrome, joint infection, hemophilia, hemochromatosis, or neuropathic arthropathy of any cause.
- 25. Patients with radiographic (plain X-ray or MRI) evidence of disease that would impact the ability of the study to meet its primary or secondary objectives; examples include the following:
 - Patients with a history of osteonecrosis or who are deemed to have or have risk factors for rapid progression of OA, including sub-chondral insufficiency fracture or spontaneous osteonecrosis of the knee
 - Patients with recent fractures (stress, pathologic, or traumatic) defined by the presence of a visible fracture line
 - Patients with cystic lesion 0.5 × the femoral or tibial subchondral plate
 - Patients with a history of pigmented villonodular synovitis
- 26. Patients who previously received treatment in a UBX0101 study.
- 27. Patients who have received another investigational drug or investigational vaccine within the last 3 months prior to Screening.
- 28. Patients who are participating in or are planning to participate concurrently in another investigational drug or vaccine study.
- 29. Female patients who are pregnant, lactating, or of childbearing potential who do not agree to use highly effective methods of birth control (e.g., progesterone-only hormonal contraception, double barrier, or intrauterine device) for 3 months following the last dose of Study Drug. Postmenopausal females (> 45 years old and without menses for more than 1 year) and surgically sterilized females are exempt from these requirements.
- 30. Male patients who do not agree to use a highly effective method of contraception for 3 months following the last dose of Study Drug, if sexually active with a female partner of childbearing potential.

5.5 Lifestyle Restrictions

5.5.1 Fluid and Food Intake

There are no restrictions of fluid or food intake during the study. Patients should be encouraged to maintain their usual diet and fluid intake as much as possible, to avoid any potential confounding impact on the study endpoints.

5.5.2 Patient Activity Restrictions

Patients will not be required to be confined during the course of this study; however, on Day 1, the patient will be required to have an electrocardiogram (ECG) collected prior to Study Drug administration. Additionally, on Day 1 of Study Drug administration, patients will remain in the clinical unit until the 2-hour postdose blood collection for PK assessment.

Patients should refrain from moderate exercise or physical exertion for 48 hours prior to entering the study on Day 1 (day of Study Drug administration). After the IA Study Drug injection, patients will be advised to rest, to avoid ambulation as much as possible for the first 4 hours, and to avoid significant exertion for the first 24 hours after IA injection.

6 STUDY CONDUCT

6.1 Study Procedures

6.1.1 Study Screening and Treatment Periods

The Screening period is 35 days, and the treatment and follow-up period is 24 weeks (from randomization and Study Drug administration to the final follow-up visit).

Patients will be followed-up for up to 24 weeks.

Patient clinic visits are scheduled as follows: Screening, Visit 1/Week 0/Day 1, Visit 2/Week 1/Day 8, Visit 3/Week 2/Day 15, Visit 4/Week 4/Day 29, Visit 5/Week 8/Day 57, Visit 6/Week 12/Day 85, Visit 7/Week 18/Day 127, and Visit 8/Week 24/Day 169.

The visit window is ± 10 days for Visits 4 through 8 (Weeks 4 through 24).

In consideration of the COVID-19 outbreak, investigative sites and patients affected may conduct some visits remotely. The asterisks (*) below indicate the critical assessments to be completed remotely and the remaining assessments will not be considered as deviations but should be documented as a "missed assessment with Sponsor approval". If clinical judgement of the investigator and local recommendations allow, patients may complete Week 12 and Week 24 Visits in clinic.

6.1.1.1 Screening Period/Day -35 to -1

- · Obtain informed consent
- Review eligibility criteria
- Record demographics
- Review medical history
- Perform medication review (including concomitant medication)
- Administer WOMAC
- Administer Patient Global Assessment (PGA)
- Perform pregnancy test
- Perform urine drug screen
- Perform physical examination
- Perform knee examination
- Measure vital signs
- Perform laboratory tests (hematology and chemistry)
- Perform knee x-ray
- Perform MRI
- Patients to be trained on completing the NRS Daily Pain question on the e-diary

6.1.1.2 Visit 1/Week 0/Day 1

- Review eligibility criteria
- Review medical history
- Randomization
- Perform medication review (including concomitant medication)
- Administer WOMAC
- Administer PGA
- Administer Multidimensional Psychological Questionnaire (MPsQ)
- Perform physical examination
- Perform knee examination
- Measure vital signs
- Perform ECG
- Perform urine pregnancy test
- Perform laboratory tests (hematology and chemistry)
- Conduct blood biomarker sampling
- Conduct urine biomarker sampling
- Administer study drug
- · Conduct AE assessment
- Conduct pharmacokinetics blood sampling

6.1.1.3 Visit 2/Week 1/Day 8 (±5 days)

- Perform medication review (including concomitant medication)
- Administer WOMAC
- Perform knee examination
- Measure vital signs
- Perform laboratory tests (hematology and chemistry)
- · Conduct AE assessment
- Review NRS Daily Pain response

6.1.1.4 Visit 3/Week 2/Day 15 (±5 days)

- Perform medication review (including concomitant medication)
- Administer WOMAC
- · Measure vital signs
- Conduct AE assessment

Review NRS Daily Pain response

6.1.1.5 Visit 4/Week 4/Day 29 (±10 days)

- Perform medication review (including concomitant medication)*
- Administer WOMAC*
- Measure vital signs
- Perform laboratory tests (hematology and chemistry)
- Conduct AE assessment*
- Review NRS Daily Pain response*
- Conduct blood biomarker sampling
- Conduct urine biomarker sampling

6.1.1.6 Visit 5/Week 8/Day 57 (±10 days)

- Perform medication review (including concomitant medication)*
- Administer WOMAC*
- Measure vital signs
- Conduct AE assessment*
- Review NRS Daily Pain response*
- Conduct urine biomarker sampling

6.1.1.7 Visit 6/Week 12/ Day 85 (±10 days)

- Perform medication review (including concomitant medication)*
- Administer WOMAC*
- Administer PGA*
- Administer PGIC*
- · Perform knee examination
- Measure vital signs
- Perform laboratory tests (hematology and chemistry)
- Conduct blood biomarker sampling
- Conduct urine biomarker sampling
- Conduct AE assessment*
- Review NRS Daily Pain response*

6.1.1.8 Visit 7/Week 18/Day 127 (±10 days)

Perform medication review (including concomitant medication)*

- Administer WOMAC*
- Measure vital signs
- Conduct AE assessment*
- Review NRS Daily Pain response*

6.1.1.9 Visit 8/Week 24/ Day 169 (±10 days), Final Follow-Up

- Perform medication review (including concomitant medication)*
- Administer WOMAC*
- Administer PGA*
- Administer PGIC*
- · Perform physical examination
- Perform knee examination
- Measure vital signs
- Perform laboratory tests (hematology and chemistry)
- Perform serum pregnancy test
- Conduct blood biomarker sampling
- Conduct urine biomarker sampling
- Perform knee x-ray
- Perform MRI (scan may occur 14 days prior to Visit 8 visit to allow for scheduling flexibility)
- Conduct AE assessment*
- Review NRS Daily Pain response and de-activate e-diary*

6.1.1.10 Unscheduled Visits and Early Termination

- Perform medication review (including concomitant medication)*
- Administer WOMAC*
- Administer PGA*
- Administer PGIC (Early Termination only)*
- Perform physical examination
- Perform knee examination
- Measure vital signs
- Perform laboratory tests (hematology and chemistry)
- Perform serum pregnancy test
- Conduct blood biomarker sampling

- Conduct urine biomarker sampling
- Conduct AE assessment*
- Review NRS Daily Pain response and de-activate e-diary (Early Termination only)*

6.1.2 Informed Consent

It is the responsibility of the Investigator to obtain signed written consent for the study from each patient prior to participating in the study to provide for the protection of the patients by following applicable regulations and institutional policies and procedures. The Informed Consent Form (ICF) used during the informed consent process must be reviewed by the Sponsor or designee and approved by the Institutional Review Board (IRB)/Independent Ethics Committee (IEC).

6.1.3 Medical History and Medication Review, Including Concomitant Medications

A detailed medical history will be obtained by the Investigator or qualified designee. This will include a comprehensive medical history and a complete review of systems, with specific attention to inclusion and exclusion criteria. Past medical history deemed by the Investigator as not clinically relevant to the patient's overall health status or to his or her OA will not be captured. Relevant medical history will be recorded in the electronic case report form (eCRF).

Medications taken until the time of randomization will be recorded as part of the patient's medical history. Medications taken after randomization will be recorded as concomitant medications.

Particular attention will be given to analgesic use history.

6.1.4 Pregnancy Test

Serum pregnancy tests will be performed at a central laboratory at Screening and Final Follow-up (Visit 8/ Week 24) or Early Termination. Urine pregnancy (dipstick) tests will be performed predose on the dosing day (Week 0) and ad hoc at physician's discretion (Table 1).

6.1.5 Physical Examination

Physical examination includes assessments of the skin, head and neck, lungs, heart, abdomen, lymph nodes, extremities, and body weight. Height will be measured at Screening only.

Complete physical examinations will be performed by a licensed physician (or a physician's assistant or nurse practitioner) at Screening and Final Follow-up (Visit 8/ Week 24) or Early Termination. Symptom-directed physical examinations are required to be performed as clinically indicated.

6.1.6 Knee Examination

At the Screening visit and Day 1 knee examinations, there will be a detailed examination of the target knee by the Investigator or qualified designee. The target knee will be examined for erythema, warmth, tenderness, swelling, effusion, crepitus, laxity, and range of motion.

6.1.7 Vital Signs

Vital signs (blood pressure, respiratory rate, pulse rate, and oral temperature) will be obtained in the sitting position. The patient must be in the sitting position for 5 minutes prior to obtaining vital signs.

6.1.8 Electrocardiography

Evaluation will be performed prior to administration of Study Drug for baseline reference. Guidance for performing the ECG evaluation will be included in the ECG manual.

6.1.9 Patient-Reported Outcomes

WOMAC, PGA, and PGIC will be conducted prior to vital signs, physical exams, ECGs, and blood draws. Average daily pain NRS will be collected via an e-diary.

- WOMAC
- PGA
- PGIC
- Average daily pain NRS

6.1.10 Patient Phenotyping Questionnaire

Multidimensional Psychological Questionnaire (MPsQ)

- MPsQ will be collected predose at Visit 1/Week 0/Day 1. To be conducted prior to vital signs, physical exams, ECGs, and blood draws.
- The MPsQ is a questionnaire derived from other validated personality questionnaires that evaluates patient's personality, well-being as well as attitudes and beliefs on disease therapies. It evaluates the likelihood of placebo response.
- MPsQ is self-reported by each patient and each item is rated on a 5-point scale ranging from 1 (strongly disagree) to 5 (strongly agree). The MPsQ used in this study includes 119 questions that are divided into 2 parts to allow some break between parts. Approximately 35 minutes are needed to complete the MPsQ in its entirety.

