In terms of clinical responses, patients treated with single IA injections of UBX0101 had clinically meaningful and dose-dependent improvements in knee pain symptoms as measured by the average daily pain NRS (0–10 point scale) and the WOMAC-A (Likert scale, 0–4) at 12 weeks compared to those who received placebo treatment. In a prospectively defined analysis in which the placebo (n = 14), low dose combined 0.1 through 0.4 mg UBX0101 (n = 16), and high dose combined 1 through 4 mg UBX0101 (n = 18) groups were compared, the least squares (LS) mean of the change from baseline (CFBL) in NRS at Week 12 was significantly greater for the high dose UBX0101 group (-3.95, p < 0.01) compared to the placebo (-1.96) and low dose groups (-2.66, p = 0.42 versus placebo). Especially for the UBX0101 4 mg highest dose group, LS mean reductions from baseline in the NRS of 4 points and greater up to Week 12 suggested a large magnitude UBX0101 treatment effect. Similarly, pain reduction as measured by WOMAC-A was clinically meaningful and greater in the high dose UBX0101 group compared to the placebo and the low dose groups. For the higher doses, the pain responses appeared to be durable through 12 weeks. The improvements in pain NRS over time in Part A are presented in Figure 2.

[figure not shown]

Figure 2 NRS Weekly Least Squares Mean Change From Baseline to Week 12

CFBL=change from baseline; LS=least squares; NRS = numeric rating scale; SE=standard error.

Clinically meaningful, dose-dependent improvements in physical function as measured by the Western Ontario and McMaster Universities Osteoarthritis Index function subscale (WOMAC-C) were observed and were greater in UBX0101-treated patients compared to those who received placebo. Evaluation of Patient Global Impression of Change (PGIC) following UBX0101 treatment demonstrated a higher proportion of patients being "much improved" or "very much improved" versus placebo at 12 weeks (placebo = 42.9%, low doses of UBX0101 [0.1, 0.2, and 0.4 mg] = 50.0%, high doses of UBX0101 [1.0, 2.0, and 4.0 mg] = 61.1%).

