7.2.3 Extent and Maintenance of Blinding

This study will be double-blind; Investigator and Patient will be blind to the treatment assigned. However, the site pharmacist will be required to prepare Study Drug and will therefore have knowledge of the treatment code; the site pharmacist is otherwise not involved in any study

procedures. Sponsor personnel or any designee who is actively engaged with the site will remain blinded.

Treatment will be prepared and dispensed by the unblinded site pharmacist in accordance with the randomization schedule provided by the Sponsor and administered electronically through the randomization system. The site pharmacist may not be involved with the study procedures, assessments, or data recording and will not reveal the randomization code to anyone. The Study Drug will be administered to the target knee through IA injection by an appropriately qualified blinded injector (this individual may be the Investigator or a nominated Sub-Investigator) in the clinic.

It is of importance to ensure that patients are blind to the treatment received; it is recognized that the method of administration of IA injection has the propensity to contribute to a placebo response (Altman et al. 2016), and therefore, maintaining the blind for patients, Investigators, and study personnel who assess patients will assist in minimizing this bias.

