9.1.1 Sample Size Determination

Each of the four arms of the Phase 2 design are planned to have approximately 45 patients per group. The target number of patients per group randomized and treated was chosen to facilitate 40 patients per group completers for the 12 week primary endpoint of WOMAC-A score assuming a 10% dropout rate. The sample size was calculated based on Phase 1 WOMAC-A effect size and variability as measured by the mean and standard deviation of the least square mean differences between the treated groups and placebo at Week 12.

In the Phase 1 study, which included five to six UBX0101-treated patients per arm, there was an observed WOMAC-A effect size compared to placebo ranging from 0.2 to 0.7 and a standard deviation ranging from 0.2 to 0.4 on the 0–4 item subscore.

The sample size estimation for Phase 2 was a result of assuming a power of 90% and an alpha of 0.10 for a two-sample, two-sided comparison with an effect size of 0.50 (treated versus placebo) on the WOMAC-A item score (0–4) least square mean at 12 weeks with an assumed standard deviation of 0.75 to account for increased variability in a larger sample size, greater number of sites, and broader patient population under study compared with the previous Phase 1 study.

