9.1.3 Analysis of Efficacy Endpoints

The change from baseline to Weeks 12 and 24 of the WOMAC-A, NRS, and WOMAC-C will be analyzed based on details provided in the Statistical Analysis Plan.

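### Does collecting a 119-item placebo-response questionnaire with no stated analysis role waste precision in the primary comparison?

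*Combined protocol and SAP*

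**What the plan says.** Section 6.1.10 (Patient Phenotyping Questionnaire) schedules the MPsQ once, predose at Visit 1. It has 119 items on a 5-point scale, covers personality, well-being, and attitudes and beliefs about therapies, and is derived from other validated questionnaires. Its stated purpose is: "It evaluates the likelihood of placebo response".

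Elsewhere the MPsQ appears only as an abbreviation, a row and footnote in Table 1 (Schedule of Events), and an item in the Visit 1 list. It is absent from the synopsis objectives, Table 2, Section 7.2.2 (randomization, which names no stratification factor) and all of Section 9.

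Section 7.2.3 acknowledges placebo response: "it is recognized that the method of administration of IA injection has the propensity to contribute to a placebo response". It then offers maintenance of the blind as the measure that helps limit the resulting bias.

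On the efficacy analysis, Section 9.1.3 says only that change from baseline in WOMAC-A, NRS and WOMAC-C "will be analyzed based on details provided in the Statistical Analysis Plan". Sections 9.1.2.2, 9.1.4 and 9.3 likewise send baseline characteristics, exploratory analyses and further analysis details to the SAP.

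Section 9.1.1 sizes the trial with "an alpha of 0.10 for a two-sample, two-sided comparison", 90% power, a difference of 0.50 on the WOMAC-A item score and "an assumed standard deviation of 0.75".

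**The concern.** The protocol takes placebo response to an injection seriously, and Section 2.1.3 reports a mean NRS improvement of 1.96 points in Phase 1 placebo patients. It asks about 180 patients to spend some 35 minutes on an instrument aimed at that response, and then says nothing about using the answers.

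A pre-treatment variable that predicts outcome can be put in the primary model without biasing the randomized comparison, and it narrows the intervals for all three dose contrasts at no cost in patients. Leaving out a useful one means wider intervals than necessary.

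There is also an integrity worry. An instrument of 119 items with no stated score, cut-off or role could later be searched for a subgroup of low placebo responders in whom the drug looks better. With three doses against placebo and a two-sided alpha of 0.10, such a finding would be hard to interpret.

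**Working it through.** **1. The plan's own figure.** Inputs from Section 9.1.1: difference 0.50, SD 0.75, two-sided alpha 0.10, power 90%, dropout 10%.

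n per group = 2 × (z₀.₉₅ + z₀.₉₀)² × (SD/difference)² = 2 × (1.645 + 1.282)² × (0.75/0.50)² = 38.5, rounded up to 39.

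The exact t calculation gives power of 89.8% at 39 and 90.5% at 40, so 40 completers are needed. Then 40/0.90 = 44.4, rounded up to 45 per group, and 4 × 45 = 180. The stated sample size reproduces. It is a plain two-sample calculation that takes no credit for any covariate, so it owes nothing to the MPsQ.

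**2. What adjustment could add.** If a baseline score explains a share R² of the residual variance, the residual SD becomes 0.75 × √(1 − R²), the standard error of one active-placebo contrast becomes that SD × √(2/40), and the equivalent unadjusted sample size is 40/(1 − R²). The documents give no R² for the MPsQ, so the range below is an assumption. Power is exact t at 40 per arm, two-sided alpha 0.10.

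| Assumed R² | Residual SD | SE of contrast | Equivalent n per arm | Power, difference 0.50 | Power, difference 0.40 |
|---|---|---|---|---|---|
| 0 | 0.750 | 0.168 | 40 | 90.5% | 76.4% |
| 0.05 | 0.731 | 0.163 | 42 | 91.7% | 78.3% |
| 0.10 | 0.712 | 0.159 | 44 | 92.9% | 80.2% |
| 0.20 | 0.671 | 0.150 | 50 | 95.1% | 84.1% |

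The 0.40 column is a sensitivity case inside the Phase 1 range of 0.2 to 0.7 quoted in Section 9.1.1. At the planning difference the gain is 91.7 − 90.5 = 1.2 points to 95.1 − 90.5 = 4.6 points.

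**3. Which R² matters.** The relevant share is the increment over baseline WOMAC-A, which any sensible model of change would already contain. The table applies R² to the full planning SD of 0.75. Section 9.1.1 attaches that SD to a least square mean, so it may already reflect some adjustment. Both points make the table the favourable end.

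**4. Does Phase 1 support a large R²?** The −1.96 is a mean, on the NRS, in 14 placebo patients. A mean shift does not say how much patients differ from one another, and a placebo response shared equally by all arms cancels in the active-placebo difference. Nothing in the documents shows that differences in placebo response are the main source of variance in WOMAC-A change. A score built to predict placebo response may also predict less well in the active arms, so one common R² for all contrasts is a further assumption.

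**5. Is there a score to adjust for?** Section 6.1.10 gives item scaling but no composite, and Section 2.1.3 does not report that Phase 1 collected the MPsQ. If no external algorithm existed, a predictive score would have to be trained on this trial's own outcomes, which conflicts with fixing it before unblinding.

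**6. What silence in Section 9 shows.** Section 9 names no covariate, not even baseline WOMAC-A. Absence of the MPsQ from a section that lists no covariates tells us nothing particular about the MPsQ.

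**The case for a change.** The strongest argument for acting does not depend on R². A long instrument without a stated score or role leaves room for choices after the data are seen, and a covariate picked after unblinding would carry little weight. Writing the scoring rule and role into the SAP needs no new data. The statistical price of a useless covariate is also trivial: one error degree of freedom out of 4 × 40 − 4 = 156, which moves power by less than 0.01 of a percentage point. And if the true difference were 0.40, an R² of 0.10 would lift power from 76.4% to 80.2%, which is worth having.

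Much of this stands. The protocol states no use for the MPsQ, the arithmetic is right, and it is good practice to settle scoring, role and handling of missing scores before unblinding. But the protocol assigns such detail to the SAP, and nothing in the reviewed text shows that the SAP fails to provide it. The protocol makes no subgroup claim based on the MPsQ, and any unplanned one would be read as post hoc. The argument also supports stating a role of some kind. It does not establish that the role should be covariate in the primary model: experienced statisticians would reasonably differ on putting an undefined composite there instead of treating it as exploratory or supportive.

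**Conclusion.** No change to the plan follows. What can be shown is a missing detail: the protocol collects the MPsQ without naming its score or purpose in analysis, and refers the analyses to an SAP that is not in the text reviewed. That is a gap analysts fill as a matter of course.

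The claim of wasted precision is not established. The possible gain runs from zero to about 4.6 points of power at the planning difference, and every value above zero rests on an assumed R² (up to 0.20), on that R² being incremental to baseline WOMAC-A, on its being the same in all arms, and on a usable score existing beforehand. The documents support none of these. Followed as written, the plan gives an unbiased randomized comparison with 90.5% power at 40 completers per arm under its own assumptions, which meets its stated 90%. Nothing is contradictory or miscalculated.
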